### 9.6 Analysis of Non-Access Hospitalization Rate or Death

The effects of the treatment interventions on the rate of non-access hospitalizations or death will be analyzed by treating the non-access hospitalizations and death as correlated event-time outcomes under a semi-parametric survival analytic framework. An Anderson-Gill model for recurrent events will be used to characterize the effects of the interventions on the intensity rate for the non-access hospitalizations, and a Cox-proportional hazards model will be used to characterize the effects of the interventions on the hazard rate for mortality. The joint analysis of both outcomes will be stratified by type of outcome (non-access hospitalization vs. mortality) to allow for potential differences between the baseline hazard function for mortality and the baseline intensity function for non-access hospitalizations. The models for both outcomes will be stratified also by Clinical Center, with treatment group and the pre-specified covariates included as independent variables. A common treatment effect will be modeled for both outcomes in order to produce a pooled estimated treatment effect across the two outcomes. Standard errors will be estimated using robust "sandwich-type" estimates to account for correlations of (possibly) multiple events within the same patient. Followup time will be censored at death for the non-access hospitalization outcome and at time of transplantation, transfer to a nonparticipating dialysis facility, or the end of the 12-month follow-up period for both the non-access hospitalization and death outcomes. Censoring at transplant and transfer to nonparticipating dialysis units is necessary because hospitalizations will not be recorded or classified following these events. The incorporation of death as a separate event in addition to non-access hospitalizations is intended, in part, to reduce the risk of bias due to informative censoring.

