## 2.2 Overview of Study Design

This will be a randomized, unblinded study of six times per week nocturnal home hemodialysis versus three times per week conventional home hemodialysis. A target of 90 patients will be enrolled into this study with equal allocation in each arm, stratified by Clinical Center and diabetic status. All patients will be assessed for suitability for nocturnal home hemodialysis using a standardized method prior to patients entering the baseline portion of this protocol. The minimum dialysis dose in the conventional home arm will be an equilibrated Kt/V of 1.1.In the nocturnal arm there will be a minimum prescription of six hours per session for six days per week AND a minimum achieved standard Kt/V of 4.0. Patients will be followed for 12 months.

Because no previous randomized trials of nocturnal dialysis have been conducted, the first calendar year after the initiation of enrollment has been designated as a "Vanguard" phase during which feasibility of randomization and conduct of the interventions will be evaluated. If pre-defined benchmarks for establishment of feasibility are achieved during the Vanguard phase, the trial will proceed to its primary objective of determining if 6 times per week nocturnal hemodialysis results in clinically significant improvements in physiological, health-related quality of life (HRQL) and functional outcomes, as compared with three times per week conventional home hemodialysis.

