#### 2.4 Recruitment Strategy

#### 2.4.1 Description of Centers and Available Patient Pool

The target sample size for this trial is 90 patients, of whom 50% will be randomized to nocturnal home six times per week hemodialysis. Patients will be recruited from designated Clinical Centers in the United States and Canada (See Figure 2), which have a combined pool of more than 11,000 prevalent dialysis patients. Each Clinical Center will have the capacity to recruit a minimum of 20 patients into the trial. Data from the Lynchburg and Saratoga Springs nocturnal home hemodialysis programs suggest that between 5 to 10% of patients within their dialysis units have been trained and started on nocturnal home hemodialysis. Other programs have noted that a similar percentage of patients have initiated nocturnal home hemodialysis. [Piccoli, 2002]

Several programs in our consortium have accepted patients from outside of their own dialysis units for home hemodialysis training purposes. In Saratoga Springs, NY, patients travel from as far as 300 miles away for training and for the monthly follow-ups required of home training patients. This situation is similar to that described in Iowa City, IA, where home hemodialysis patients travel up to 300 to 400 miles for training and for monthly follow-up.

Each of the Clinical Centers in this consortium has contacted adjacent nephrology programs and dialysis units and has obtained permission to recruit patients from these units for a study in home nocturnal dialysis. Based on information provided from the Clinical Centers and the adjoining dialysis units, we have provided below in Table 2 a summary of the number of patients that will be available for recruitment into the nocturnal study from this clinical trials consortium.

Clinical Center	Number	Blacks	Whites	Males	Females	Other*	Total
Lynchburg, VA	336	210	126	184	152	400	736
Saratoga Springs, NY	333	27	296	173	160	1020	1353
New York City, NY (Rogosin Inst.)	565	245	149	283	282	600	1165
St. Louis, MO (Washington U)	683	499	118	311	372	730	1413
Kansas City, MO	367	145	220	194	183	400	767
Winston-Salem, NC (Wake Forest)	1169	625	517	596	575	650	1819
London, Ontario, Canada	566	17	515	300	266	0	566
Indianapolis, IN (Indiana U)	441	309	128	216	225	30	741
Iowa City, IA (U of Iowa)	186	10	166	93	93	680	866
U of Toronto -Toronto General Hospital	445	50	185	267	178	180	625
Humber River Regional Hospital	303	77	151	161	124	0	303

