As described in Section 9.3, the PHC/Mortality and LV mass/Mortality composites are the coprimary endpoints for evaluation of patient benefit in the trial. In addition, as described in Section 5.1.2, main secondary outcomes have also been designated for each of seven specific and conceptually distinct physiological or quality of life-related outcome domains. These include: i) change over 12 months in the PHC; and, ii) change over 12 months in LV mass (without the mortality components), which represent the main secondary outcomes for evaluation of the physical function and cardiac structure and function domains, respectively. The remaining outcome domains and associated main secondary outcomes are iii) depression/disease burden (change over 12 months in Beck Depression Inventory), iv) nutrition (change over 12 months in serum albumin), v) cognitive function (change over 12 months in the Trails B), vi) mineral metabolism (change over 12 months in average pre-dialysis phosphorus), and vii) clinical events (rate of non-access hospitalizations or death). The primary evaluation of the effects of the treatment interventions on each of these seven outcome domains will be based on the designated main secondary endpoints. Analyses of other outcomes within each domain will be regarded as exploratory. Hypertension and anemia are also stipulated as main outcome domains, but are not conducive to the designation of a single main endpoint.

Two-sided tests will be used when testing the effects of the interventions on both the primary and secondary endpoints. The primary and main secondary analyses will be conducted by intention-to-treat in the sense that all patients analyzed according to their randomized assignment, irrespective of whether they adhered to the interventions. As noted above, however, follow-up will be censored at the time of renal transplantation. The analyses of the main secondary endpoints will be tested at the 0.05 level, without formal adjustment for multiple comparisons. However, nominally significant effects on individual secondary outcomes will be interpreted as consistent with Type I errors unless accompanied by significant effects of the interventions on the primary outcomes and a consistent pattern of treatment effects across multiple secondary outcomes.

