### 9.5 General Analytic Strategy for Quantitative Outcomes

The following analytic strategy will be employed for quantitative outcomes, including each of the main secondary outcomes with the exception of the rate of non-access hospitalization or death. The main analysis for each outcome will evaluate the treatment effect on the change from baseline to 12 months. For outcomes evaluated monthly (serum albumin and pre-dialysis phosphorus) the 12 month value will be averaged over the Months 10, 11, and 12 assessments for increased statistical power. For each outcome with multiple follow-up assessments (including the PHC, serum albumin, Beck Depression Inventory, Trailmaking Test B, and pre-dialysis phosphorus), an additional analysis will be conducted to evaluate the change from baseline to Month 4, where the Month 4 value is taken as the average value over months 3, 4, and 5 for serum albumin and pre-dialysis phosphorus. The analysis of change to 4 months will evaluate short term effects, while the analysis of change to 12 months will evaluate longer-term effects. The 4-month comparison is also intended to evaluate treatment effects prior to significant attrition. The "basic model" to be used for quantitative outcomes is:

$$\Delta \mathbf{Y}_{t} = \beta_{0t} + \beta_{1t} \operatorname{Trt} + \beta_{2t} \mathbf{Y}_{0} + \Sigma \gamma_{it} \mathbf{S}_{i} + \Sigma \delta_{it} \mathbf{F}_{i} + \varepsilon_{t}, \quad (\text{Basic Model})$$

where  $\Delta Y_t$  denotes the change in the response variable from baseline to time t, Trt is an indicator variable for the daily treatment intervention,  $Y_0$  is the baseline value of the response variable, the  $S_i$  are indicator variables for the Clinical Centers, the  $F_i$  are the following six pre-specified baseline covariates (age, race, years of dialysis, diabetic status, baseline serum albumin, and

FHN Nocturnal Protocol Version 3.3: October 15, 2008

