## 9.9 Missing Data

In spite of the relatively short follow-up of 12 months, a nontrivial loss-to-follow-up is inevitable in a study of HD due to high rates of death, transplant, and patient transfer to non-participating facilities. In the HEMO Study the combined loss-to-follow-up from death, transplant, and transfer was approximately 18% at 1 year.

Because all methods for accounting for missing data are subject to bias depending on untestable assumptions [Verbeke, 2000], efforts will be made to minimize missing data in the study design and conduct of the trials [Allison, 2001]. These include: 1) continuing data collection after safety stop-points or patient-termination of the treatment regimens, 2) provisions to obtain the key outcome results at a later time point should the patient be hospitalized at the target time for the visits, 3) monitoring and feedback regarding missing data throughout the trial, and 4) oral

administration of questionnaires.

Analytically, including prognostic baseline covariates and the early 4-month follow-up assessment should also reduce the chance of significant bias from missing data under the restricted maximum likelihood approach we propose. In this approach, bias from missing data at the 12-month assessment is reduced to the extent that relationships between the unobserved values of missing responses and the probability of missingness can be accounted for by either the baseline factors or the observed 4-month responses. [2014 FHN Archive Note: FHN Executive Committee dropped prognostic covariates from the analyses.] Nonetheless, some bias due to informative censoring [Little, 1995] is probably inevitable. Therefore, we plan to use a pattern mixture approach [Little, 1995] to perform sensitivity analyses of the estimated treatment effects under a range of assumptions regarding the association of the censoring times with the values of the missing responses [Daniels, 2000].

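### With 90 patients, the sandwich-based test of non-access hospitalization or death in Section 9.6 needs a small-sample correction: the usual Wald version runs at about 6–12%, not 5%

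*Protocol*

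**What the plan says.** Section 9.6 treats non-access hospitalizations as recurrent events and death as a single event, with one treatment effect common to both. Beyond the stratification by event type, it states: "The models for both outcomes will be stratified also by Clinical Center, with treatment group and the pre-specified covariates included as independent variables". The standard errors are robust sandwich "estimates to account for correlations of (possibly) multiple events within the same patient". It mentions neither a finite-sample correction nor a reference distribution, and rules out neither.

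The covariates are the "six pre-specified baseline covariates (age, race, years of dialysis, diabetic status, baseline serum albumin, and" baseline GFR of Section 9.5. An archive note in Section 9.9, repeated in substance in Section 2.7, says that the "FHN Executive Committee dropped prognostic covariates from the analyses". Section 9.6 itself carries no such note.

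On the level, Section 9.4 says: "Two-sided tests will be used when testing the effects of the interventions on both the primary and secondary endpoints", and "The analyses of the main secondary endpoints will be tested at the 0.05 level, without formal adjustment for multiple comparisons". On size, Section 2.2 says: "A target of 90 patients will be enrolled into this study with equal allocation in each arm".

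The endpoint's rank is contradictory. Table 7 and the second, seven-item list in Section 9.4 count it as a main secondary outcome. Section 5.1.3.5 says it is not one, for want of power, and the first list in Section 9.4 omits it.

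**The concern.** A sandwich variance is consistent as the number of independent patients grows. With few patients it tends to be too small, because the residuals it is built from have been shrunk by the fit. Here the fit is demanding: up to seven terms, and risk sets split by event type and by center, so each comparison is made among a handful of patients. Referring the resulting ratio to the normal distribution then rejects too often and gives intervals that cover too seldom.

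At stake are the p-value and interval for the only first-priority outcome made up wholly of clinical events. Section 5.1.1 also plans to work out the chance of one, two or more positive main secondary results under a joint null. If that calculation takes each test at its nominal 0.05, an inflated test would distort it.

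**Working it through.** **Inputs from the Protocol.** 90 patients allocated 1:1 (Sections 2.2 and 2.4.1); 12 months of follow-up; admission rate 1.19 per year less 40%, i.e. 1.19 × 0.60 = 0.714 per year; mortality 7% per year; transplantation 6% per year (all Section 9.11). The number of centers is unclear: Section 2.3 speaks of eight, while Table 2 has twelve rows. Both were used, giving 90/8 ≈ 11 or 90/12 = 7.5 patients per center.

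**Assumptions not in the Protocol.** Transfer 6% per year; between-patient gamma heterogeneity with variance 0 to 2; covariate distributions and effects.

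**Expected events.** Without heterogeneity, the total exit rate is 0.07 + 0.06 + 0.06 = 0.19 per year. Mean follow-up is (1 − e^−0.19)/0.19 = 0.911 years, or 90 × 0.911 = 82 patient-years. That gives 0.714 × 82 ≈ 58.5 admissions and 0.07 × 82 ≈ 5.7 deaths, about 64 in all. The simulations gave 61–64, and 62 at variance 1.

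**The stated figure.** The plan's figure is a size of 0.05. Trials were simulated under no treatment effect, with permuted blocks within center and diabetic status and the Section 9.6 model fitted to each (4,800–6,000 trials per setting, Monte Carlo error 0.3–0.4 points). As a check of the code, the model-based test of the seven-term model with no heterogeneity rejected in 4.5–5.0% of trials, as it should.

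**Size of the patient-clustered sandwich Wald test against ±1.96:**

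| Heterogeneity variance | 12 centers, six covariates | 8 centers, six covariates | 12 centers, none | 8 centers, none |
|---|---|---|---|---|
| 0 | 9.4% | 7.4% | 7.2% | 5.8% |
| 0.5 | 9.9% | 9.5% | not run | 6.8% |
| 1 | 11.3% | 10.0% | 8.5% | 7.8% |
| 2 | 12.0% | 10.9% | 9.0% | 8.1% |

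Ten centers at variance 1 gave 10.5% with covariates and 7.4% without. Using the unreduced rate of 1.19 per year (ten centers, with covariates) gave 9.9%. Separately written simulation code gave 8.1–11.6% with covariates under heterogeneity (7.6% with none) and 6.4–8.3% without covariates.

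**Why it happens.** If the mean robust standard error is r times the true standard deviation, the size is roughly 2Φ(−1.96r). At variance 1:
- 12 centers with covariates, r = 0.799: 2Φ(−1.566) = 11.7%, against 11.3% simulated.
- 8 centers with covariates, r = 0.837: 2Φ(−1.641) = 10.1%, against 10.0%.
- 12 centers without, r = 0.873: 2Φ(−1.711) = 8.7%, against 8.5%.
- 8 centers without, r = 0.899: 2Φ(−1.762) = 7.8%, against 7.8%.

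So the low standard error accounts for nearly all of the excess. Across the table r runs from 0.780 to 0.894 with covariates and from 0.863 to 0.954 without. Coverage of the nominal 95% interval is one minus the size: about 88–93% and 91–94%.

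**What drives it.** At variance 1, removing the center strata lowers the size to 7.3% with covariates and 5.8% without, so strata and covariates both contribute. At 250 patients (12 centers, covariates) it is 7.1%. Dropping the sandwich is no remedy: at variance 1 the model-based test ran at 13–15% in the 8- and 12-center settings.

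**Effect of corrections (seven-term model).** A leverage-corrected (Mancl-DeRouen type) sandwich with a t reference gave 4.7–7.5%. Scaling the sandwich for terms and strata, with a t reference, gave 4.9–8.0%. In a separate set of 700 trials randomized within center, a within-center permutation test gave 5.6% (Monte Carlo error about 0.9 points) against 10.7% for the Wald test on the same trials.

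**The case against.** The strongest reply is that the Protocol never says the sandwich estimate is uncorrected. The choice of correction and reference distribution is ordinary SAP detail, and the SAP is not at hand. That stands, so the point is conditional on the usual Wald test being used. It does not remove the point. The Protocol itself fixes the model, strata, terms, type of standard error and level. Section 9.5 defends validity at 90 patients and promises simulations, but only for the quantitative outcomes, from which this endpoint is expressly excepted. Section 9.6 has no counterpart.

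A reader might go further and infer that the error rate simply is about 10%, double the stated level, because the method was designed for 250 patients and not revisited. The documents do not support that. The figure depends on heterogeneity and covariate distributions that they do not give, on twelve centers where Section 2.3 says eight, and on covariates that the archive notes say were dropped. Section 9.6 gives no sample size. Section 9.4 does still project 125 patients in the standard arm, but at 250 the simulated size was still 7.1%, so the reduction to 90 explains only part. Nor does the Protocol say that this model will serve the other hospitalization rates in Section 5.1.5.5.

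It is also fair that little rests on this p-value. Section 9.4 reads an isolated significant secondary result as consistent with Type I error unless the primary outcomes and a pattern of secondary results agree, and Section 8.4 concedes low power for hospitalizations. That limits the consequence. It does not repair an interval that is too narrow.

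**Conclusion.** The concern holds in conditional form. Applied to 90 patients with the usual sandwich Wald test, Section 9.6 gives a true two-sided size of about 7–12% with the six covariates and about 6–9% without them, where Section 9.4 states 5%. The interval is too narrow in proportion. The size exceeded 5% in every uncorrected 90-patient scenario in the table, although with eight centers, no covariates and no heterogeneity the excess is under one point. The exact value rests on 8–12 centers, heterogeneity variance 0–2, 6% per year transfer and assumed covariate distributions. This is a moderate point about a secondary endpoint of contradictory rank. It does not touch the co-primary analyses.

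**What to change.** In Section 9.6, keep the pooled treatment estimate and change how its uncertainty is assessed:

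1. Take the p-value from a re-randomization test that follows the actual randomization strata, Clinical Center and diabetic status (Section 2.9). Permuting within center alone would not reproduce the design. The 5.6% result above is for center alone; the two-factor version was not simulated here.
2. At the least, use a leverage- or degrees-of-freedom-corrected sandwich standard error with a t reference. Use that standard error for the confidence interval in either case, and say which result governs if the p-value and interval disagree.
3. State whether the six covariates remain in this model. Dropping them reduces the inflation but does not remove it.

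Reconcile Section 5.1.3.5 with Table 7 and Section 9.4 on the endpoint's rank at the same time.

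The cost is a paragraph and a few lines of code, with larger p-values and wider intervals. Restoring the standard error means dividing by r, i.e. about 12–28% wider with covariates (1/0.894 to 1/0.780) and 5–16% without (1/0.954 to 1/0.863). The analytic correction alone leaves the size at about 5–8%, which is why the re-randomization p-value is preferred.

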### 9.7 Analysis Strategies for Other Outcomes

A modified version of the basic model for Bernoulli response variables will be used to analyze the change in the rates of dichotomous outcomes such as the presence of intradialytic hypotensive episodes [Diggle, 1994]. Primary unassisted patency will be defined as the time from randomization until the first access procedure or thrombosis (including angioplasty), and analyzed by Cox regression stratified by Clinical Center with treatment group and the pre-specified covariates as independent variables [Klein, 1997].

Ordinal variables will be analyzed using longitudinal models adapted for ordinal categorical outcomes with repeated measurements [Liang, 1995;Toledano, 1999].

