## Safety

3) To determine the safety of the nocturnal hemodialysis intervention, with a particular emphasis on vascular access and patient burden.

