a) Vascular Access Complications: Access infection, stenosis, thrombosis, and intervention will be defined, and a detailed protocol developed to monitor and treat these complications in both groups. The primary measure of vascular access complications will be primary unassisted patency rate (time to first access intervention). Groups will also be compared with respect to: number of access interventions per patient years, time to first thrombosis related access failure, and number of thrombosis related access failures per patient years,

number of access infections per patient years, number of infection related access failures per patient years, time to first infection related access failure.

- b) Iron Losses: Patients on daily hemodialysis have been shown to have increased iron losses compared with conventional patients. Iron utilization will be documented in both groups.
- c) Malnutrition: Although it is anticipated that nutritional status will improve with nocturnal hemodialysis, the potential for malnutrition exists. There may be increased dialytic losses of amino acids due to increased clearances provided with nocturnal hemodialysis. Thus, nutritional status, as outlined in Sections 5.1.3.3 and 5.1.5.3, will be monitored on a regular basis.
- d) Patient Burn-Out: Patient fatigue is a potential concern with the increased frequency of treatments with nocturnal hemodialysis, especially with the requirement that the patients perform the dialysis treatments themselves. The proportion of patients who require a change in dialysis modality lasting more than 2 weeks (back to conventional hemodialysis or to peritoneal dialysis) will be assessed along with reasons for modality change.
- e) Calcium and phosphorus balance: Nocturnal hemodialysis is known to decrease serum phosphate and even lead to hypophosphatemia. Persistently low serum phosphate may lead to weakness, osteomalacia and severe hypophosphatemia (defined as a serum level < 1.0 mg/dl) may cause hemolysis, acute respiratory failure, myocardial depression, or seizures. In addition, nocturnal hemodialysis can lead to negative calcium balance due to calcium loss through ultrafiltration. This may lead to increase of PTH and alkaline phosphatase. These laboratory parameters will be monitored on a regular basis as outlined in Section 3.4.1.d.

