#### 6.3.4 Vascular Access Complications

All vascular accesses will be tracked for complications using a modification of the Dialysis Access Consortium (DAC) Study vascular access forms. A form will be completed on each patient at the time of randomization that will classify the type and location of the vascular access in use at that time. A vascular access complication form will be completed whenever the study patient undergoes one or more of the following vascular access procedures: access failure (thrombosis or removal requiring placement of a new access), placement of a new vascular access, access intervention (angioplasty, stenting, surgical revision, fibrin sheath stripping, etc., but not TPA instillation or venogram only). The procedures performed for these access complications will also be noted on this form. Vascular access infections not requiring removal of the access will not be recorded. Information on vascular access complications will be provided to the DSMB to monitor the rates of access complications in each arm of the study.

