baseline GFR), and the  $\varepsilon_t$  are random residuals at t = 4 and 12 months. The primary focus of the model will be to estimate the treatment effect  $\beta_{1t}$  as accurately as possible; the remaining terms are included to reduce residual variability and reduce bias from missing data. The model will be fit by restricted maximum likelihood [Harville, 1977] assuming an approximate normal distribution and with an unstructured covariance matrix for the residuals at the two time points. The change in the LV mass from baseline to its single follow-up assessment at 12 months will be analyzed by restricting the basic model to one time point, which simplifies to traditional analysis of covariance.

The target sample size of 90 patients is sufficient that inferences for the fixed effect terms in these analyses will remain valid with moderate departures from normality [Verbeke, 1997]. However, standard diagnostics will be performed and simulations conducted to address this issue, and modifications to the model will be made if necessary. In addition to evaluating the effects of the treatment interventions on LV mass, in grams, the effects of the interventions on the percentage change in LV mass will also be considered in secondary analyses.

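### The Cox model for primary unassisted patency omits access type at randomization, which is recorded for every patient; entering it as a covariate would modestly improve the main vascular-access safety analysis

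*Protocol*

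**What the plan says.** The safety objective in Section 2.1 is to establish the safety of nocturnal hemodialysis "with a particular emphasis on vascular access and patient burden". Section 5.3(a) ranks the access outcomes: "The primary measure of vascular access complications will be primary unassisted patency rate (time to first access intervention".

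Section 9.7 fixes the model. Patency time is "analyzed by Cox regression stratified by Clinical Center with treatment group and the pre-specified covariates as independent variables". The only list of pre-specified covariates is in Section 9.5: "the following six pre-specified baseline covariates (age, race, years of dialysis, diabetic status, baseline serum albumin, and" baseline GFR. Access type is not on that list. It is not a randomization stratum (Section 2.9 uses Clinical Center and diabetic status) and not one of the interaction factors in Section 9.8.

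The variable is nevertheless collected. Under Section 6.3.4 every patient has a form at randomization "that will classify the type and location of the vascular access in use at that time". Section 2.5.2 excludes only temporary non-tunneled catheters, and Section 5.3 describes safety devices for catheters and for grafts or fistulas, so the protocol expects all three types.

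A 2014 archive note in Section 9.9 adds: "FHN Executive Committee dropped prognostic covariates from the analyses".

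**The concern.** Time to first access intervention depends on the access a patient starts with, partly because the events that can be counted depend on it. Section 5.1.5.6 ties thrombolytic use to fistulas and grafts. Section 6.3.4 counts angioplasty, stenting, surgical revision and fibrin sheath stripping, but not TPA instillation. Patients with different accesses are therefore exposed to different sets of qualifying procedures.

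Section 9.7 borrows a covariate list written for the change-score model of Section 9.5, where the covariates serve partly to reduce residual variability. That same purpose argues for access type in the patency model. At stake is the precision of the main access-safety comparison: lower power to see harm, a hazard ratio drawn toward 1 (for a safety outcome, the direction that understates harm), and an estimate that moves with whatever imbalance in access type the randomization produces.

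**Working it through.** **No figure of the plan to reproduce.** The protocol states no event count, hazard ratio or power for patency. As a check on the sample-size basis only, Table 15 gives 16.0 g at SD 24 for 80% power. With 90 × 0.80 / 2 = 36 measured per arm, 16.0 / (24 × √(2/36)) = 2.83 and Φ(2.83 − 1.96) = 0.807, which agrees.

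**Inputs from the protocol.** 90 patients, 1:1, so 45 per arm; 12 months of follow-up; 7%/yr mortality plus 6%/yr transplantation (Section 9.11), so 13%/yr censoring; Cox model stratified by center.

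**Assumptions not in the protocol.** True treatment hazard ratio (HR) 2 (or 1 for the null); access mix; event rates; access-type hazards; 10 center strata (Section 2.3 mentions eight centers and Table 2 lists twelve). The six general covariates were not simulated. Each scenario used 1,500 trials, so one power figure has a Monte Carlo standard error of about √(0.5 × 0.5 / 1500) = 1.3 points.

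**Step 1: validity.** With a true HR of 1 and 10 center strata, the rejection rate was 3.8% to 6.0% without access type and 4.4% to 5.9% with it. The planned test is valid.

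**Step 2: three access types entered as a covariate.** True HR 2, 10 center strata, fistula event rate 0.35/yr, and fistula/graft/catheter shares of 50/15/35% except in the last row.

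| Graft / catheter hazard vs fistula | Mean events | Power without → with | Median HR without → with |
|---|---|---|---|
| 1 / 1 | 33.9 | 45.5% → 46.4% | 1.97 → 2.00 |
| 1.5 / 2 | 42.5 | 53.1% → 53.9% | 1.94 → 2.02 |
| 2 / 3 | 48.0 | 51.3% → 57.9% | 1.84 → 2.02 |
| 3 / 5 | 53.9 | 48.6% → 62.6% | 1.75 → 2.03 |
| 2 / 3, shares 70/10/20% | 42.3 | 51.1% → 54.4% | 1.92 → 2.04 |

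**Step 3: covariate or stratum.** With two access levels, 40% catheters, low-risk rates of 0.3 and 0.5/yr, true HR 2 and 10 center strata:

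- As a covariate, access type adds about 2 to 3 points of power at an access-type HR of 2, 5 to 9 at 3, and 9 to 14 at 4. It costs under 1 point at 1.
- As center-by-access strata, power at an access-type HR of 3 goes from 51% to 47% and from 57% to 56% for the two event rates. Across the scenarios it falls or stays about level in nearly every case; the exception was an access-type HR of 4 at rate 0.5 (54% to 58%). Three access types by 10 centers would leave 90 / 30 = 3 patients per stratum on average.

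**Step 4: chance imbalance.** With 40% catheters, the standard error of the between-arm difference in catheter share is √(2 × 0.4 × 0.6 / 45) = 0.103. A difference of at least 15 points has two-sided probability 0.146 (z = 0.15 / 0.103 = 1.45). If catheters carry three times the hazard and the shares are 47.5% and 32.5%, the crude HR with no treatment effect is (1 + 0.475 × 2) / (1 + 0.325 × 2) = 1.95 / 1.65 = 1.18.

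The simulations with 35% catheters agree. An imbalance of 15 points or more occurred in 13% to 17% of trials. A 15-point excess in the nocturnal arm multiplied the unadjusted HR by 1.09 to 1.10 at twofold catheter hazard, 1.15 to 1.17 at threefold and 1.19 to 1.23 at fivefold. After adjustment the factor was 0.98 to 1.01.

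**The case against.** The strongest reply is that nothing here is invalid. One common covariate set across outcomes is a defensible choice, the test holds its level, and chance imbalance is already part of the random error that the confidence interval describes. In size, ln 1.18 = 0.166, while with 48 events the standard error of the log HR is about 2/√48 = 0.29, so the example imbalance is a little over half a standard error. Half of the 15% probability falls in each direction. The movement toward 1 reflects non-collapsibility: the marginal and the access-conditional hazard ratios are different quantities. All of this stands, and it limits the point to precision, attenuation and conditional imbalance.

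It is also true that no decision rests on this model alone. Section 5.3(a) lists further access measures, access complication rates by arm go to the DSMB (Section 6.3.4), and Section 10.3 ties no stopping rule to this hazard ratio.

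The reply that covariates belong in the SAP does not stand. Section 9.7 states the model and Section 9.5 closes the list at six, so the protocol has made the choice.

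Three stronger readings may tempt a reader:

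- **The analysis is biased.** Step 1 shows that it is not, over repeated randomizations.
- **Access type should become a stratum, with large gains.** A log-rank calculation that ignores centers suggests gains such as 52% to 60% or 61% to 72% at an access-type HR of 3. The plan stratifies by center, and Step 3 shows that those gains then disappear.
- **The archive note proves an error in Section 9.7.** It is a later annotation. The point stands without it, because access type was never on the list.

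**Conclusion.** The point holds in modest form. The model for the primary access-safety measure omits a baseline variable that the trial records for every patient and that helps determine which events can occur. If access type is prognostic, some power is given up, the hazard ratio moves toward 1 (from 2.0 to 1.94, 1.84 or 1.75 at twofold, threefold or fivefold catheter hazard in the three-type runs), and the estimate is exposed to imbalance among 90 patients.

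The size cannot be fixed from the protocol, which gives no access mix, event rates or access-type hazards. The power at stake runs from none when access type is not prognostic to about 14 points at the strongest hazards assumed, and it shrinks when catheters are few. Adjustment would not make the comparison well powered: in the 10-center, three-type runs where access type matters, power for an HR of 2 remains about 54% to 63%.

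**What to change.** In Section 9.7, add access type at randomization (fistula, graft, tunneled catheter) as a covariate in the center-stratified Cox model for primary unassisted patency. Do the same for the access-intervention and access-failure rates. Do not make it a further stratum. Reporting patency by access type descriptively would help interpretation.

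The cost is one sentence and one or two more model terms, with no new data collection, since the form in Section 6.3.4 already holds the variable. Specifying it in advance also avoids a contestable post hoc adjustment if the arms turn out unbalanced.
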